5.1.1. Missing Data Handling Procedure

When conspicuity assessment cannot be performed, conspicuity score will be missing. Reason for each Not Assessed cases will be documented in the database.

- For the primary analysis (Table 14.2.1.1), missing data will not be imputed. Subjects will be included in the input dataset as is. This analysis will be referred to as the Observed Data Analysis.
- However, the impact of missing data will be evaluated by performing 3 sensitivity analyses. The sensitivity analysis will use the same model specified for the primary analysis; nominal p-values from each sensitivity analysis will be reported as. Those 3 sensitivity analyses are described below:
 - Sensitivity Analysis 1 – This analysis will include all MITT subjects who have no missing data. That is, all subjects in this analysis will have 4 conspicuity scores as planned (Table 14.2.1.2).

- Sensitivity Analysis 2 – This analysis will exclude all subjects who are not in the PP population and subjects who have ≥ 1 missing data. This would represent the best outcome for the study since all potential confounded issues will be removed (Table 14.2.1.3).
- Sensitivity Analysis 3 – This analysis will impute the missing data that creates the worst scenario for the study (Table 14.2.1.4).
 - Missing data for Saline Treatment: Assign missing value for saline treatment to be the best value from this patient if scores are available. If no score is available for this patient, then assign the best score of 5 to missing data.
 - Missing score for IC Treatment: Assign missing value for IC treatment to the worst score the patient had if scores are available. If none is available, assign the worst score of ‘1’ to missing data.

5.2. PSAS with IC Treatment

Each subject will have 1 PSAS score. Ratings in the PSAS with the IC treatment will be tabulated (**Table 14.2.2**) by treatment (IC High dose, IC Low dose, and overall (pooled across high dose and low dose) with number (%) subjects in each rating category and overall satisfactory.

Two-sided 95% confidence intervals on proportion of physicians who are satisfied (with ratings 1 or 2) will be derived using the Wilson confidence limits for the binomial proportion. This is also known as score confidence limits. The Wilson interval has been shown to have better performance than the Wald interval and the exact (Clopper-Pearson) interval (SAS Users' manual).

A binomial 1-way proportion approach will be used to examine that $\geq 50\%$ of the physicians are satisfied with the IC treatment (a superiority test) as an aid for the assessment of ureter patency comparing to the saline treatment. Below is an example of SAS syntax to implement this analysis.

```
DATA psas;
  Set PSASscore;
  If score in (1, 2) then psasC='1Yes'; else psasC='2No';
Run;
PROC SORT data=psas; BY trt psasC;
PROC FREQ DATA=psas ORDER=DATA;
  TABLES psasC / BINOMIAL(SUP P=0.45 MARGIN=0.05 CL=WILSON) alpha=.05;
  BY trt;
  ODS OUTPUT BinomialCLs=bCL
    BinomialSup=pval
  ;
run;
```

This syntax makes the 'Yes' response to be the first category so the binomial test will examine the proportion of response in the Yes category. The null proportion of 0.45 and margin of 0.05 makes the point estimate of superiority limit to be 0.50 (superiority limit = the null proportion + margin). The 'TRT' is coded to 'High', 'Low' or 'All'. 'All' includes subjects from both IC High and IC Low doses.

An exploratory analysis to examine any difference in PSAS with the use of IC High dose vs the IC Low dose will be performed via a Cochran-Mantel-Haenszel (CMH) test for 'Row Mean Scores Differ'. Below is an example of SAS syntax to implement this analysis

```
PROC FREQ DATA=psas;
  TABLES dose*psas / noproct CMH2 alpha=.05;
  ODS OUTPUT CMH=pval
  ;
run;
```

where 'dose' is coded to Low or High; the 'PSAS' is the satisfaction rating score (1, 2, 3, 4, or 5).

Normal p-value for each analysis will be reported as is without controlling for multiple comparisons.

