2. OVERVIEW OF STUDY OBJECTIVES AND ASSESSMENTS

The primary objective of this study is to determine whether the use of Indigo Carmine 0.8% Injection, USP solution for injection (IC) provides a visualization advantage compared to saline when used as an aid in the determination of ureteral patency. Visualization will be measured by a 5-point conspicuity score as follows:

- 1 = No jet observed
- 2 = Weak jet, little color contrast
- 3 = Color contrast or significant jet flow
- 4 = Strong jet flow with good color contrast
- 5 = Strong jet flow with striking contrast in color

Secondary objectives are to assess:

1. To evaluate the safety profile of IC when used as an aid in the determination of ureteral patency.
2. To determine physicians' overall satisfaction with the IC treatment by assessing the proportion of surgeons who agree using the 5-point Physician Satisfaction Agreement Scale (PSAS) with the statement:

“Compared to the saline treatment, my ability to assess ureter patency was improved after the addition of IC.”

- 1. Strongly Agree
- 2. Agree
- 3. Neither Agree nor Disagree
- 4. Disagree
- 5. Strongly Disagree

A surgeon's evaluation is considered satisfactory if the rating is either a 1 (strongly agree) or 2 (agree).

3. To determine proportion of responders. To determine proportion of subjects meeting the responder definition in conspicuity score following IC treatment based on the blinded central reviewer's assessment. A subject is a responder when there is ≥ 1 point difference in the conspicuity score following the IC vs saline treatment (IC – Saline ≥ 1) and the conspicuity score following the IC treatment is (3, 4, or 5). The responder criteria will be assessed separately for each ureter for each subject.

4. To describe the time to visualization (TTV) of blue color in the ureteral jets flow following IC treatment when used as a visualization aid during urological and gynecological surgical procedures
5. To determine the IC pharmacokinetic profile in a subset of subjects from 2 investigational sites.
6. An exploratory comparison will be done on the difference between the IC high dose vs IC low dose. Surgeons will be blinded to the dose of IC.

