The study will enroll approximately 116 subjects from approximately 10 – 20 study centers in the United States. Subjects scheduled for urological or gynecological surgical procedures, age 18 to 85 years inclusive, will be screened for participation. Screening will occur within 30 days before study drug administration (Day of Surgery). After signing the informed consent, medical history, physical examination, baseline laboratory testing, pregnancy testing, 12-lead ECG, and vital sign measurements will be completed during the screening visit. Any procedure done for the purpose of the surgery before the date of signing the informed consent may be used as long as it was within 30 days of the scheduled surgery date.

On the day of surgery (Day 1) the subject will be evaluated for eligibility for randomization. Eligible subjects will be randomized to receive a dose of either IC high dose (5 mL) or IC low dose (2.5 mL). Each randomized subject will serve as his/her own control by receiving a dose of normal saline prior to receiving the randomized IC dose. The surgeon will be blinded to the IC dose a subject receives. Time of injection of saline and IC will be captured.

To evaluate the efficacy outcomes, each subject will first be injected intravenously with 5 mL 0.9% saline. The ureteral orifices/flow will be observed and video recorded for 10 mins. The time period that will be captured on video is from injection to 10 minutes post injection. If both ureters cannot be visualized simultaneously, then alternating 15-30 second images of each ureter or ureteral orifice will be obtained. The process will be repeated in the same patient for the IC dose. Hence, each subject will have 2 videos and each will be about 10 minutes in length.

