2.1. Study Endpoints

2.1.1. Efficacy Endpoints

The **primary** efficacy endpoint is conspicuity score after each treatment provided by the central readers:

- 1 = No jet observed
- 2 = Weak jet, little color contrast
- 3 = Color contrast or significant jet flow
- 4 = Strong jet flow with good color contrast
- 5 = Strong jet flow with striking contrast in color

The **secondary** efficacy endpoints include:

1. Proportion of physicians who agree that compared to saline, IC treatment improves visualization as an aid for the assessment of ureteral patency
2. To determine proportion of IC treatment responders per the blinded central reviewers' assessment. A subject is a responder to the IC treatment when there is ≥ 1 point difference in the conspicuity scores between the IC and saline treatment (IC – Saline ≥ 1) and the conspicuity score following the IC treatment is (3, 4, or 5). The responder criteria will be assessed separately for each ureter for each subject.
3. Time (minutes) from start of drug administration to visualization (TTV) of the blue color in the ureteral jets flow after IC administration

Other efficacy endpoints will include:

1. Conspicuity scores assessed by the surgeons
2. Concordance of the Conspicuity scores between the surgeons' assessments and the blinded central reviewers' assessments.

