3.8.4. Physician Satisfaction Agreement Scale

After the completion of the procedure, the surgeon will be asked to rate the experience of using IC for each patient using the PSAS:

“Compared to the use of saline treatment, my ability to assess ureteral patency was improved after the addition of IC”

1 = Strongly Agree

2 = Agree

3 = Neither Agree nor Disagree

4 = Disagree

5 = Strongly disagree

The surgeon is considered satisfied with the IC treatment if his/her rating is either a 1 (Strongly Agree) or a 2 (Agree); otherwise, the surgeon is considered unsatisfied with the IC treatment.

Overall Satisfaction = Yes if PSAS is 1 or 2, otherwise

Overall Satisfaction = No

Physician who did not provide rating (missing data) will be grouped in the ‘No’ group for overall satisfaction analysis.

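### The PSAS analysis calls a per-procedure rating a proportion of physicians, and its Wilson interval and test against 0.50 ignore that one surgeon is likely to rate several patients

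*SAP*

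**What the plan says.** SAP Section 2 words the satisfaction objective as a proportion of surgeons, and Section 2.1.1 lists the endpoint as "Proportion of physicians who agree that compared to saline, IC treatment improves visualization". Section 5.2 keeps that unit: "Two-sided 95% confidence intervals on proportion of physicians who are satisfied (with ratings 1 or 2) will be derived using the Wilson confidence limits". It then tests whether at least half of the physicians are satisfied, for High, Low and all subjects pooled.

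The data have a different unit. Under Section 3.8.4, "the surgeon will be asked to rate the experience of using IC for each patient using the PSAS", and Section 5.2 opens with "Each subject will have 1 PSAS score". Table 14.2.2 counts subjects. The example PROC FREQ code takes one record per subject and has no surgeon or centre term.

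Section 2 plans "approximately 116 subjects from approximately 10 – 20 study centers", and Section 3.2 leaves about 95 of these for efficacy. On p-values, Section 5.2 says: "Normal p-value for each analysis will be reported as is without controlling for multiple comparisons".

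**The concern.** There are two linked problems.

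- **Label.** A report following Section 5.2 would give a proportion of physicians whose denominator is patients. This is visible in the text and needs no assumption.
- **Independence.** The rating is a personal opinion from a surgeon who knows which injection was the dye (Section 5.1), so ratings by one surgeon plausibly agree more than ratings by different surgeons. Wilson limits and the one-sample binomial test ignore this.

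Nothing else in the SAP covers it. Section 3.6 leaves centre out of the models and allows a centre check only at discretion, with no method. Section 5.6 concerns the primary endpoint. The GEE models in Sections 5.1 and 5.5 cluster by subject.

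At stake are the stated precision of a secondary objective, and a superiority claim if the satisfaction rate is only moderately above 50% and few surgeons give correlated ratings.

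**Working it through.** **The plan's own figure.** Superiority limit = null proportion + margin = 0.45 + 0.05 = 0.50, as stated. With n = 95 independent ratings, a one-sided 5% test passes from 56/95 (59%), with exact type I error 0.0501. The method is sound if ratings are independent.

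**Inputs from the SAP.** 116 subjects and 10 to 20 centres (Section 2); 21 excluded from efficacy (Sections 3.2 and 3.3), so n = 116 - 21 = 95, or about 48 per dose if allocation is 1:1. Ratings per centre average 95/20 = 4.75 to 95/10 = 9.5. One rating per surgeon would need about that many different surgeons at every centre. Section 2 also refers to a surgeon's patients in the plural.

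**Assumptions, not in the documents.** Number of surgeons k, ICC, and a one-sided 5% test (the side is not stated).

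**Design effect.** With m = n/k ratings per surgeon, DE = 1 + (m - 1) x ICC and effective n = n/DE. At a true 50%, rejection is roughly P(Z > 1.645/sqrt(DE)).

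- k = 40, ICC 0.1: DE = 1 + 1.375 x 0.1 = 1.14; effective n about 84; P(Z > 1.54) = 0.06
- k = 20, ICC 0.1: DE = 1 + 3.75 x 0.1 = 1.375; effective n about 69; P(Z > 1.40) = 0.08
- k = 10, ICC 0.1: DE = 1 + 8.5 x 0.1 = 1.85; effective n about 51; P(Z > 1.21) = 0.11
- k = 10, ICC 0.3: DE = 1 + 8.5 x 0.3 = 3.55; effective n about 27; P(Z > 0.87) = 0.19

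**Simulation of the planned method.** Beta-binomial, 100,000 runs per case, true 50%, even ratings per surgeon. Cells show Wilson 95% coverage / one-sided rejection.

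| Surgeons, ICC | Pooled, n = 95 | One dose, n = 48 |
|---|---|---|
| No clustering | 96% / 0.050 | 94% / 0.055 |
| 40, 0.1 | 95% / 0.063 | 94% / 0.057 |
| 20, 0.05 | 94% / 0.066 | 93% / 0.062 |
| 20, 0.1 | 92% / 0.080 | 92% / 0.070 |
| 10, 0.1 | 87% / 0.114 | 89% / 0.087 |
| 10, 0.3 | 72% / 0.195 | 80% / 0.141 |

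Uneven workloads make it worse: 20 surgeons with 1 to 20 ratings each, ICC 0.1, n = 95 gives 87% / 0.115.

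**Surgeons taken as fixed.** With 10 surgeons whose spread matches ICC 0.1 or 0.3, mean Wilson coverage is 96% or 98%. For that target there is no defect.

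**Surgeon-clustered GEE (specified under the fix).**

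- Even ratings, true 50%, 10 to 40 surgeons, ICC 0.05 to 0.3, both sample sizes: coverage 95.5% to 96.6%, rejection 3.8% to 4.8%.
- Uneven ratings (largest surgeon 30, 20 or 10 of 95 among 10, 20 or 40 surgeons; ICC 0.1 and 0.3): coverage 91.7% to 94.5% and rejection 0.054 to 0.074, against 58.6% to 92.5% and 0.078 to 0.259 as planned.
- True 90%, n = 95: coverage 90% to 96%, against 73% to 96% as planned.

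**High versus Low.** With dose randomised by subject and ICC 0.3, two-sided 5% rejection is 0.050 with 10 surgeons and 0.052 with 20. The exploratory CMH comparison is not affected.

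**The case against.** The strongest reply is that the defect depends on a target the SAP does not state, and on two numbers it does not give. If only the participating surgeons matter, Wilson is adequate. Several surgeons per centre are possible, since the trial takes "Subjects scheduled for urological or gynecological surgical procedures"; with 40 surgeons and ICC 0.1 the planned method is nearly right.

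The test decision is also seldom in doubt. At a true 80% with n = 95 it moves materially only with 10 surgeons and ICC 0.3 (rejection 0.99 to 0.89). At a true 90% the clustered test still rejects in at least 98% of runs with even ratings, and in 93% in the most uneven severe case. PSAS p-values are nominal, and Section 3.4 limits type I error control to conspicuity.

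Most of this stands and limits the weight of the point; it does not remove it. The SAP's own wording speaks of physicians, which supports a target wider than the procedures observed. Nominal reporting waives multiplicity control; it does not excuse a 95% interval that covers less than 95%. A high satisfaction rate protects the test but not the interval: at a true 90% with 10 surgeons and ICC 0.3, planned coverage is 73%.

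On the label, Section 5.2 does make the analysed unit clear to a careful reader. The objective, endpoint and hypothesis still name another one.

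**Conclusion.** The concern holds, as a change that should be made, with medium confidence. The mismatch between label and data is certain. The understated uncertainty is conditional on three things: a target beyond the participating surgeons, repeat rating by surgeons (likely, but its extent is not stated), and positive within-surgeon correlation. Its size runs from negligible with many surgeons to severe with 10 surgeons at ICC 0.3. The primary conclusion is not touched.

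**What to change.** 1. State the target: procedures by surgeons like those taking part. Relabel the estimate as the proportion of procedures rated satisfied in Sections 2, 2.1.1 and 5.2, and align Section 3.8.4. If only the participating surgeons are meant, say so; the Wilson limits then serve.
2. For High, Low and All, take the interval and the test against 0.50 from an intercept-only logistic GEE clustered by surgeon (by investigator if no surgeon identifier is held). Use independence working correlation, so that the estimate stays the observed proportion. Multiply the robust SE by sqrt(k/(k - 1)), use t on k - 1 df, and state the side of the test. Keep Wilson as a supportive display.
3. If all ratings in a group agree, the GEE has no finite estimate. Use Wilson limits at n/DE, with DE = 1 + (sum of m^2/n - 1) x ICC, m = each surgeon's number of ratings, and an ICC fixed in advance (for example 0.1). Base the test on whether the matching limit exceeds 0.50. With all ratings satisfied, 10 to 40 surgeons and ICC 0.05 to 0.3, the one-sided 95% limit is 0.89 to 0.95 (n = 48) or 0.91 to 0.97 (n = 95), so the ICC chosen does not alter the test result.
4. Report the number of surgeons and the ratings per surgeon.
5. Leave the High-versus-Low CMH test as it is.

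**Cost.** SAP wording, a surgeon identifier in the PSAS dataset, one small model per group and the fallback formula. Counts by investigator are already planned (Section 4.1), but the documents do not show that the rating surgeon is identified, and an investigator may not be that surgeon. If the protocol uses the same physician-level wording, it would need to match.

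Precision is lost where clustering is real (n = 95; GEE thresholds are the counts at which it succeeds about half the time):

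| | 40 surgeons, ICC 0.1 | 20 surgeons, ICC 0.1 | 10 surgeons, ICC 0.3 |
|---|---|---|---|
| Mean CI width at a true 70% (planned 0.18) | 0.20 | 0.23 | 0.38 |
| Two-sided CI excludes 0.50 from (planned 58/95) | about 59/95 | about 60/95 | about 69-70/95 |
| One-sided test rejects from (planned 56/95) | about 57/95 | about 58/95 | about 65-66/95 |
| One-sided rejection at a true 70%, planned to GEE | 0.99 to 0.98 | 0.98 to 0.95 | 0.90 to 0.57 |

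### The PSAS superiority test and its Wilson interval use different error levels, so the p-value can fall below 0.05 while the 95% interval includes 50%

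*SAP*

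**What the plan says.** SAP section 5.2 covers the Physician Satisfaction Agreement Scale (PSAS). A rating of 1 or 2 counts as satisfied, and "Each subject will have 1 PSAS score".

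- **Interval.** "Two-sided 95% confidence intervals on proportion of physicians who are satisfied (with ratings 1 or 2) will be derived using the Wilson confidence limits". The reason given is that "The Wilson interval has been shown to have better performance than the Wald interval"; the same sentence also ranks Wilson above the exact interval.
- **Test.** "A binomial 1-way proportion approach will be used to examine that" at least 50% "of the physicians are satisfied with the IC treatment (a superiority test"). The sample code is "TABLES psasC / BINOMIAL(SUP P=0.45 MARGIN=0.05 CL=WILSON) alpha=.05", and the p-value is read from the output table named in "BinomialSup=pval".
- **Threshold.** "The null proportion of 0.45 and margin of 0.05 makes the point estimate of superiority limit to be 0.50".

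The text does not give the sidedness of the test, the variance it uses, a significance level other than the code's 0.05, or what is reported if no rating is unfavourable. Section 5.2 reports p-values without multiplicity adjustment. Section 3.4 confines type I error control to the primary endpoint. Under section 3.8.4 a missing rating counts as not satisfied.

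**The concern.** A superiority test against a fixed limit has one direction. Judged at 0.05, it spends twice the one-sided error that a two-sided 95% interval spends on the same side. The interval method requested in the code sets the limits, and nothing in that line sets the variance of the test. Test and interval may therefore differ in method as well as in level.

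At stake is a results table for the first-listed secondary efficacy endpoint in which the p-value says that more than half are satisfied and the interval in the same table does not. If the test uses the sample variance, there is a second problem: a result with every rating favourable, the strongest possible, would have no p-value.

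**Working it through.** **Inputs**

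- Null proportion 0.45, margin 0.05, alpha 0.05, two-sided 95% Wilson limits: SAP 5.2.
- Pooled n about 95, that is 116 − 21: SAP 3.2.
- n per dose about 47 or 48, since 95/2 = 47.5. This assumes equal allocation, which SAP 3.7 implies by expecting the saline group to be twice the size of each dose group. I also ran every n from 40 to 58, and pooled n of 90, 95, 96 and 116.
- Assumed: p is judged against 0.05, because no other level is given.

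**The plan's own figure.** 0.45 + 0.05 = 0.50. It reproduces.

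**Formulas**, with p̂ = x/n:

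- Sample-variance (Wald) test: z = (p̂ − 0.50)/√(p̂(1 − p̂)/n)
- Null-variance (score) test: z₀ = (p̂ − 0.50)/√(0.25/n)
- The Wilson 95% lower limit exceeds 0.50 exactly when z₀ > 1.96, that is, when the score test rejects at one-sided 0.025.

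**One case in full: 29 of 47.** p̂ = 0.6170. Wald: 0.1170/0.0709 = 1.650, one-sided p = 0.049. Score: 0.1170/0.0729 = 1.605, one-sided p = 0.054. Wilson interval: 47.4% to 74.2%.

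**Counts around the threshold**

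| Satisfied | Wald p (one-sided) | Score p (one-sided) | Wilson 95% |
|---|---|---|---|
| 29/47 | 0.049 | 0.054 | 47.4% to 74.2% |
| 30/47 | 0.024 | 0.029 | 49.5% to 76.0% |
| 31/47 | 0.010 | 0.014 | 51.7% to 77.8% |
| 30/48 | 0.037 | 0.042 | 48.4% to 74.8% |
| 31/48 | 0.017 | 0.022 | 50.4% to 76.6% |
| 56/95 | 0.038 | 0.041 | 48.9% to 68.3% |
| 57/95 | 0.023 | 0.026 | 49.9% to 69.3% |
| 58/95 | 0.014 | 0.016 | 51.0% to 70.3% |

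With the Wald form at 0.05, rejection starts at 29/47, 30/48 and 56/95. With the null variance at 0.05 it starts at 30/47, 30/48 and 56/95. The interval excludes 50% only from 31/47, 31/48 and 58/95. At every n tried, under either variance, at least one count rejects while the interval includes 50%.

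**Exact size.** This is the binomial tail at p = 0.50 from the first rejecting count, Wald form at 0.05: 4.0% (n = 40), 6.8% (45), 7.2% (47), 5.6% (48), 4.3% (49), 4.4% (58), 5.0% (95). Over n = 40 to 58 it lies between 4.0% and 7.2%, rising and falling with discreteness.

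**All ratings favourable.** With p̂ = 1 the sample variance is 1 × 0/n = 0 and z has no value. The score test still gives z₀ = 0.5/√(0.25/48) = 6.93 for 48/48, and the Wilson lower limit is 92.6%. The chance of this outcome at n = 47 depends on the true rate, which the SAP does not give: 0.95⁴⁷ = 9% and 0.97⁴⁷ = 24% for assumed rates of 0.95 and 0.97.

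**The case against.** The strongest reply is that this is a difference of convention on an endpoint for which no formal error claim is made. The SAP states no success rule for PSAS, reports nominal p-values, and calls its code an example. A reader would see the Wilson interval next to the p-value. The conflict is also narrow. At n = 47 it occurs only at 29 or 30 satisfied, with probability 22% if the true rate is 60%, 14% at 70% and 0.6% at 80%. All of this stands and sets the priority. It does not remove the inconsistency, because the code is the only specification of the test and the prose offers no other level.

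Two stronger readings are tempting and are not supported:

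- *The test always exceeds its nominal 5%.* It does not. The size is 7.2% at n = 47 but 4.3% at n = 49 and 5.0% at n = 95. What holds at every n tried is that it exceeds the 2.5% implied by the interval.
- *The test certainly fails when all ratings are favourable.* That follows only if the sample variance is used. The SAP does not state the variance, and the remark preferring Wilson to Wald is about intervals. In that case the Wilson limits would still be reported, and one missing rating, counted as not satisfied, would remove the zero variance.

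**Conclusion.** The point holds as an inconsistency of level between the planned test and the planned interval. It rests on reading the superiority test as one-sided and on judging p against the coded 0.05; it does not depend on the variance formula. It affects one or two counts at each sample size tried, at about 58% to 65% satisfied. The size range and the counts unique to the Wald form, such as 29/47, depend on the sample variance, as does the missing value at 100%. The figures per dose also assume roughly equal groups.

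Priority is minor. PSAS is secondary and outside type I error control, and satisfaction well above 65% would make the conflict irrelevant.

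**What to change.** In section 5.2, replace the superiority-with-margin request by the score (null-variance) test of a proportion of 0.50 at one-sided 0.025. State the sidedness, variance and level in the text, and label the p-value as one-sided. This test rejects exactly when the lower two-sided 95% Wilson limit exceeds 0.50 (from 31/47, 31/48 and 58/95), and it has a value when every rating is favourable.

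An exact binomial test at one-sided 0.025 is an alternative but is not the same rule. It agrees at n = 47 and n = 95 but needs 32/48 where the Wilson rule needs 31/48. The score test's exact size is 2.0% at n = 47 and 3.0% at n = 48, so a team that wants strict control at 2.5% would choose the exact test and accept occasional disagreement with the Wilson limits. One of the two should be named before database lock.

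The cost is one line of code, a sentence or two of text, and a threshold one or two ratings stricter.
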